Upon determination of the pharmacologically active dose or MTD, or when the maximally intended dose is reached, up to 10 additional patients may be enrolled at this dose level to confirm the assessment and to collect additional safety, PK and PD data to aid in determining the recommended dose of APR-246 in combination with venetoclax and rituximab.

Table 3. APR-246 Dose Levels

Dose Modification	APR-246 Dose
Dose Level 1	APR-246 1.5 g/day 0.5 g (for first 45 minutes) + 1.0 g (for 5 hours 15 minutes)
Dose Level 2	APR-246 3.0 g/day 1.0 g (for first 45 minutes) + 2.0 g (for 5 hours 15 minutes)
Dose Level 3	APR-246 4.0 g/day 1.33 g (for the first 45 minutes) + 2.66 g (for 5 hours 15 minutes)

Prior to initiation of study treatment with APR-246 administered IV in combination with venetoclax and rituximab (during treatment cycles 2-7), patients will receive APR-246 alone on Day 1 and Day 2 of the 7-day monotherapy lead-in period, during which PK and PD of APR-246 following IV and PO administration will be evaluated. On Day 1 of the monotherapy lead-in period, APR-246 will be administered IV at the assigned cohort dose. On Day 2, APR-246 will be administered PO at the dose of 500 mg. This dose may be increased based on emerging PK data to determine dose linearity after oral dosing. Patients will be required to fast for at least 10 hours prior to APR-246 PO administration. Furthermore, a sub-group of patients may receive an oral dose of APR-246 in combination with a standard high-fat meal to determine the effect of food on APR-246 absorption.

Additional dose levels may be explored if warranted based on emerging DLT, safety, PK, and/or PD data. In addition, patients who have received at least 3 cycles of therapy at the assigned dose cohort level may advance to the next higher dose level once the next higher dose level has been declared safe by the DRT.

Responses will be assessed according to response criteria for RT ([Appendix V](#)) via blood, BM, and imaging (positron emission tomography [PET]/computed tomography [CT]). Response assessments are to be performed every 3 cycles and PET-CT scanning is recommended. For patients who achieve CR, imaging may be omitted, and minimal residual disease (MRD) assessment will be completed using flow cytometry and/or molecular techniques from the BM and/or peripheral blood.

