5.1.4 Dose-Limiting Toxicity

All TEAEs are relevant to the determination of DLTs unless they are clearly and solely due to the disease under study. The DLT evaluation period will be up to 91 days (7 days of APR-246 monotherapy plus 84 days for Cycle 1-3 with combination therapy) after the first dose of APR-246 is administered. A DLT is defined as any of the following TEAEs using the National Cancer Institute Common Terminology Criteria for Adverse Events (NCI-CTCAE), as follows:

- Any neurologic toxicity of grade 4
- Any grade ≥ 3 non-hematologic toxicity except for:
 - First occurrence of grade 3 electrolyte abnormalities and/or creatinine CL decrease resolving to grade 2 (or baseline if baseline is grade ≥ 2) within 48 hours with supportive treatment.
 - Grade 3 fatigue, nausea, vomiting, diarrhea or other manageable constitutional symptom(s) that is/are responsive to supportive therapy.
 - Grade 3 infection responding to appropriate antimicrobial therapy.
 - Any neurologic toxicity of grade 3 that does not return to grade ≤ 1 or baseline within 7 days.
- Any grade ≥ 3 hematologic toxicity will be considered a DLT except for:
 - Grade 3 neutropenia without fever
 - Grade 4 neutropenia without fever lasting 8 days or less
 - Grade 3 thrombocytopenia that does not result in bleeding or transfusion
 - Grade 3/4 lymphopenia/lymphocytosis
 - Grade 3/4 WBC decreased
 - Grade 3/4 WBC increased

Any toxicity, regardless of the NCI-CTCAE v5.0 grade, resulting in discontinuation, dose reduction or treatment with less than 75% of planned doses of APR-246 study drug, will be reviewed by the DRT, and will be considered a DLT unless clearly and solely related to the disease under study. The DRT will consist of the Medical Monitor, Site Principal Investigators, and other clinical research personnel that the Sponsor may deem appropriate.

G-CSF support for the management of neutropenia and prophylactic antimicrobial therapy are allowed, including during the DLT period.

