^a During APR-246 monotherapy lead-in, ECG should be collected in triplicate within 30 minutes prior to the infusion of APR-246 and within ±30 min of end of the 6-hour infusion (EOI) of APR-246 on Days 1 – 2. QTcF must be calculated from a mean of all three ECG readings.

If a patient starts treatment with a medication associated with QT interval prolongation, such as triazole antifungals, fluoroquinolones, and anti-emetics, while receiving study treatment, an additional pre- and post-dose (within 30 minutes prior to the infusion of APR-246 and within ±30 min of 6 hours after start of infusion) ECG should be performed on the next APR-246 treatment day.

5.3.2.4 Management Guidelines for APR-246 Dose Modifications and Criteria for Treatment Interruption and Re-Initiation with Treatment-Related Adverse Events

Table 10. Recommendations for APR-246 Dose Modifications and Criteria for Treatment Interruption and Re-Initiation with Treatment-Related Adverse Events

Renal Toxicities

Parameter	Worst toxicity ¹	Dose Modifications for APR-246
Serum Creatinine	Grade 1 (<1.5 × baseline)	Maintain dose level
	Grade 2 (>1.5-3.0 × baseline)	Omit dose until resolved to grade ≤1, then: If first occurrence, then maintain dose level If second or more consecutive occurrence, then ↓ 1 dose level
	Grade 3 (>3.0-6.0 × baseline)	Omit dose until resolved to grade ≤1, then: ↓ 1 dose level If not resolved or resolved in >7 days, evaluate if other contributing factors are present. If none, or after consideration of best interest of the patient, discontinue patient from APR-246. If other factors present, consider continuing after ↓ 1 dose level
	Grade 4 (>6.0 × baseline)	Permanently discontinue patient from APR-246

¹ Common Terminology Criteria for Adverse Events (CTCAE) version 5.

Hepatic Toxicities ¹

Parameter	Worst toxicity ²	Dose Modifications for APR-246
Bilirubin ³	Grade 1 (>ULN-1.5×ULN)	Maintain dose level with LFTs ⁴ monitored as per protocol
	Grade 2 (>1.5-3.0×ULN) with ALT or AST ≤3.0×ULN	Omit dose until resolved to grade ≤1, then: If resolved in ≤7 days, if first occurrence, then maintain dose level If second or more consecutive occurrence or if resolved in >7 days, then ↓ 1 dose level

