³ For patients with Gilbert's syndrome, these dose modifications apply to changes in direct bilirubin only.

⁴ LFTs include albumin, ALT, AST, total bilirubin (fractionated if total bilirubin >2.0×ULN), alkaline phosphatase.

Other Non-Hematological Toxicities

Toxicity	Worst toxicity ¹	Dose Modifications for APR-246
Infusion-Related Reaction	Grade 1	Maintain dose level.
	Grade 2	Maintain dose level; Symptomatic management (e.g., antihistamines, corticosteroids, narcotics, IV fluids)
	Grade 3	If resolved (to grade ≤1) in <4 hours with treatment interruption and medical therapy (e.g., antihistamines, corticosteroids, narcotics, IV fluids), continue same dose level and rate. If not resolved in < 4 hours despite treatment interruption and maximal medical therapy, stop infusion and ↓ 1 dose level for subsequent dose
	Grade 4	Permanently discontinue patient from APR-246.
	Grade 1	Maintain dose level. Monitor subject and provide supportive care measures as clinically indicated.
Nausea, Vomiting, and/or Diarrhea	Grade 2	Interrupt APR-246 dosing and monitor subject; treat promptly. Resume at current dose level if toxicity resolves to grade ≤1 or baseline, with or without use of supportive care measures, within 72 hours of onset. If toxicity does not resolve to grade ≤1 within 72 hours despite maximal medical intervention(s), then reduce APR-246 by 1 dose level once the

Toxicity	Worst toxicity ¹	Dose Modifications for APR-246
		toxicity resolves to grade ≤ 1 or baseline. If unable to reduce APR-246 dose, discuss with study Medical Monitor before resuming or discontinuing treatment. For subsequent doses of APR-246, pre-medication with prophylactic supportive therapy should be given if clinically indicated.

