	Grade 3	
1st occurrence: Interrupt APR-246 dosing and monitor subject; treat promptly.
 
Resume at current dose level if toxicity resolves to grade ≤ 1 or baseline, with supportive care measures, within 72 hours of onset.
 
If toxicity does not resolve to grade ≤ 1 within 72 hours despite maximal medical intervention(s), then reduce APR-246 by 1 dose level once the toxicity resolves to grade ≤ 1 or baseline.
 
If unable to reduce APR-246 dose, discuss with study Medical Monitor before resuming or discontinuing APR-246.
 
For subsequent doses of APR-246, pre-medication with prophylactic supportive therapy should be given.
 
2nd occurrence: Interrupt APR-246 dosing and monitor subject; treat promptly.
 
Reduce APR-246 by 1 dose level if the toxicity resolves to grade ≤ 1 or baseline within 72 hours of onset.
 
If toxicity does not resolve to grade ≤ 1 despite maximal medical intervention(s) within 72 hours of onset, then consult with study Medical Monitor before resuming or discontinuing APR-246.
 
If unable to reduce APR-246 dose, discuss with study Medical Monitor before resuming or discontinuing treatment.
 
Prior to subsequent doses of APR-246, reassess prophylactic supportive therapy regimen and adjust as clinically indicated.
 
3rd occurrence: Interrupt APR-246 dosing and monitor subject; treat promptly. Consult with study Medical Monitor before resuming or discontinuing APR-246.

	Grade 4	Interrupt APR-246 dosing and monitor subject; treat promptly. Consult with study Medical Monitor to discuss dose modification or permanent discontinuation of APR-246.
Any Other Toxicity	Grade 3 or 4	
Delay dose until resolution to grade ≤ 1 or baseline, then $\downarrow 1$ dose level.
 
If unable to reduce APR-246 dose, discuss with study Medical Monitor before resuming or discontinuing APR-246.

¹ Common Terminology Criteria for Adverse Events (CTCAE) version 5.

Treating physicians should use clinical judgment and may consult the Medical Monitor for additional guidance with APR-246 dose modifications.

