5.3.2.5 Management of CNS Adverse Events

If a patient reports any clinical AE of any grade during the administration period of APR-246 that could be considered to originate from the CNS (e.g., dizziness, tremor, vertigo, nausea), then the patient will be given a rescue medication as per the institutional standard of care.

Dose modifications have been successfully used to manage potential CNS effects occurring during the infusion (Table 11). For any clinical AE grade ≥ 3 , the infusion should be interrupted and if the AE resolves to CTCAE grade ≤ 1 within 2 hours, the infusion may be resumed at the same infusion rate. If

the same symptoms recur or increase in severity during re-challenge, the infusion should be interrupted.

If the event lasts longer than 2 hours, then the APR-246 infusion should be discontinued for that day and the remaining drug should be discarded.

Table 11. Management of CNS Adverse Events (e.g., Dizziness, Tremor, Confusion, and Ataxia)

Worst toxicity	Dose Modifications for APR-246
Grade 1	Maintain dose level
Grade 2	If resolved to grade ≤ 1 with medical therapy, continue same dose level If not resolved despite treatment interruption and maximal medical therapy, stop infusion and \downarrow 1 dose level for subsequent dose. If unable to reduce APR-246, discuss with study Medical Monitor before resuming or discontinuing APR-246.
Grade ≥ 3	Stop infusion and give medical therapy. If resolved (to grade ≤ 1) with medical therapy in ≤ 2 hours from onset, infusion may resume at the Investigator's discretion. If not resolved despite treatment interruption and maximal medical therapy, infusion should be discontinued for that day. \downarrow 1 dose level for subsequent dose. If unable to reduce APR-246 dose, discuss with study Medical Monitor before resuming or discontinuing APR-246.
Grade 4	Permanently discontinue patient from APR-246.

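### At 1.5 g there is no lower level to step down to, so some toxicities that count as DLTs at 3.0 or 4.0 g through dose reduction can go uncounted at Dose Level 1

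*Combined protocol and SAP*

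**What the plan says.** Section 5.1.4, repeated in the synopsis, gives a grade-based list of DLTs and then a catch-all. A toxicity of any grade "resulting in discontinuation, dose reduction or treatment with less than 75% of planned doses of APR-246 study drug" goes to the Data Review Team (DRT) and is a DLT unless the disease alone clearly explains it.

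The planned levels are 1.5, 3.0 and 4.0 g. The lowest entry in Table 3 is "APR-246 1.5 g/day 0.5 g (for first 45 minutes) + 1.0 g (for 5 hours 15 minutes". Section 4.1 adds "Additional dose levels may be explored if warranted based on emerging DLT, safety, PK, and/or PD data", but defines none below 1.5 g. The only lower dose in the readable text is 1.0 g in Table 7, for moderate renal impairment.

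The management tables foresee that a step-down may be impossible:

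- Table 10, grade 2 nausea, vomiting or diarrhea: if not resolved "within 72 hours despite maximal medical intervention(s), then reduce APR-246 by 1 dose level" after recovery, followed by "If unable to reduce APR-246 dose, discuss with study Medical Monitor before resuming or discontinuing treatment".
- Table 10, grade 3 gastrointestinal events and the row for any other grade 3 or 4 toxicity: "If unable to reduce APR-246 dose, discuss with study Medical Monitor before resuming or discontinuing APR-246".
- Table 11, grade 2 CNS events unresolved despite interruption and treatment: one level down, then "If unable to reduce APR-246, discuss with study Medical Monitor before resuming or discontinuing APR-246".
- Table 10, grade 2 creatinine: "If first occurrence, then maintain dose level If second or more consecutive occurrence, then" one level down. The grade 2 bilirubin and AST/ALT rows also direct a step-down for repeat or slow-resolving events. None of these three rows says what to do at 1.5 g.

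Under Section 4.1, 0 DLTs in 3 patients, or fewer than 2 in 6, moves the study from 1.5 g to 3.0 g. Two or more at Level 1 pause enrollment for DRT review. Two or more at a higher level make the level below the MTD.

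**The concern.** The management rules were adapted to the lowest level, but the DLT definition was not. One of its three triggers, dose reduction, is largely unavailable at 1.5 g. The same event, equally severe and persistent, can therefore be a DLT at 3.0 g and not at 1.5 g, only because no lower level exists to move to.

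The Level 1 count decides whether the dose is doubled. For these events it depends on whether the patient resumes or discontinues, not on the toxicity itself.

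**Working it through.** The plan gives no event rates or operating characteristics, so there is no figure of its own to reproduce here.

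**Step 1. Which events are affected.** The event must not be a DLT by grade, and Table 10 or 11 must direct a one-level reduction rather than suggest one.

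- Grade 2, resume route stated: gastrointestinal events beyond 72 hours; unresolved CNS events.
- Grade 2, nothing stated for 1.5 g: repeat creatinine events; repeat or slow-resolving bilirubin and AST/ALT events.
- Some exempted grade 3 events: for example, a second gastrointestinal event that responds to supportive therapy, or an infection that responds to antimicrobials and falls under the any-other-toxicity row.

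Grade 3 CNS events are left aside, because their status by grade depends on how the neurologic bullet in Section 5.1.4 is read.

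**Step 2. The same case at two levels.** Take non-serious grade 2 nausea lasting over 72 hours in 2 of the first 3 patients.

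- At 3.0 g, both are stepped down to 1.5 g. That is 2 DLTs, and 1.5 g is declared the MTD.
- At 1.5 g, both resume 1.5 g after discussion with the Medical Monitor. If each receives at least 75% of doses, that is 0 DLTs in 3, and the study advances to 3.0 g.

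**Step 3. Whether the 75% trigger catches it.** APR-246 is given on Days 1, 8 and 15, so Cycles 1–3 contain 3 × 3 = 9 IV doses. The lead-in adds one IV and one oral dose.

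| Doses counted | 2 missed | 3 missed |
|---|---|---|
| 9 (Cycles 1–3) | 7/9 = 77.8% | 6/9 = 66.7% |
| 10 (plus lead-in IV) | 8/10 = 80.0% | 7/10 = 70.0% |
| 11 (plus lead-in oral) | 9/11 = 81.8% | 8/11 = 72.7% |

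On every count, two missed doses escape the trigger and three do not.

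**Step 4. Whether Section 8.4 catches it.** The four stopping criteria need a death, a serious event in more than one patient, an event above grade 3 in more than two patients, or a lasting grade 3 or higher neurologic event. Non-serious grade 2 events meet none of them.

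**Step 5. Effect on escalation.** With DLT probability p per patient, a 3+3 cohort is passed on 0/3, or on 1/3 followed by 0/3:

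P(leave level) = (1−p)³ + 3p(1−p)²(1−p)³ = (1−p)³ + 3p(1−p)⁵.

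For example, p = 0.20 gives 0.512 + 0.197 = 0.709. All rates below are assumptions. Reduction-only events are taken to occur in patients with no other DLT, so the two rates add when the events are counted.

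| Other DLTs | Further 5% counted | Further 10% counted | Further 20% counted | None counted |
|---|---|---|---|---|
| 5% | 0.906 | 0.814 | 0.600 | 0.973 |
| 10% | 0.814 | 0.709 | 0.494 | 0.906 |
| 20% | 0.600 | 0.494 | 0.309 | 0.709 |

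The last column assumes that every affected patient resumes at 1.5 g and stays uncounted, so each contrast is an upper bound.

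**The case against.** **Breadth.** A reader might tally every entry in Tables 5, 6, 10 and 11 that mentions a step-down: nine with an unable-to-reduce clause and eight without, 17 in all. The documents do not support treating all 17 as gaps. Grade 3 bilirubin, AST/ALT and infusion reactions are DLTs by grade at every level. So are most events in Table 5. A first grade 3 gastrointestinal event that persists past 72 hours despite maximal treatment hardly fits the exemption for events responsive to supportive therapy. The Table 5 entries and the first two Table 6 entries only ask the investigator to consider a reduction. This part of the objection stands.

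**No lower dose.** A reader might infer that dose reduction can never count at 1.5 g. That goes too far. The catch-all covers any actual reduction, so a toxicity-driven Table 7 cut to 1.0 g would count, and Section 4.1 leaves room for further levels. Section 5.1.1 is redacted. Table 3 and the unable-to-reduce clauses suggest that no general lower level exists, but cannot prove it.

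**Other triggers and oversight.** Discontinuation and the 75% rule still operate at 1.5 g. The Medical Monitor sits on the DRT, which discusses all accumulated safety data. It would be wrong to say that these events go unseen. But Section 5.1.4 requires DLT review only when one of the three triggers is met, and no rule tells the DRT to count other adverse events.

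**Tolerability.** A patient who resumes 1.5 g and receives at least 75% of doses has arguably tolerated it. Table 1's title also refers to a 4.5 g infusion, above every planned level, which tempers alarm about doubling. Both points are fair, but neither explains why the same event should count at 3.0 g.

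**Conclusion.** The concern holds in a narrow form. Events that Table 10 or 11 directs to a one-level reduction, and that are not DLTs by grade, count at 3.0 and 4.0 g once the dose is stepped down. At 1.5 g they can go uncounted if the patient resumes and receives at least 75% of doses. The clearest cases are grade 2 nausea, vomiting or diarrhea beyond 72 hours and unresolved grade 2 CNS events, where the resume route is written down.

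The existence of the gap follows from the text, on the assumption that redacted Section 5.1.1 defines no lower level. Its size does not follow. A reader might take 0.71 against 0.91 as an estimate of the effect, but it is an illustration under assumed rates and the most unfavorable resumption pattern.

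**What to change.** Keep the existing catch-all and add to Section 5.1.4 and the synopsis:

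> At Dose Level 1, a toxicity for which Table 10 or Table 11 directs a one-level APR-246 reduction that cannot be made because no lower dose level exists will be reviewed by the DRT and treated as resulting in dose reduction for this criterion, whether or not dosing resumes at 1.5 g.

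Do not extend this to the entries in Tables 5 and 6 that only ask for a reduction to be considered; that would record a hypothetical judgment. The sentence can make an exempted grade 3 event a DLT at 1.5 g, but the catch-all already does so at 3.0 and 4.0 g because it applies whatever the grade. The carve-out for toxicity due only to the disease and the handling of Table 7 reductions stay as they are.

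The cost is one sentence in two places and one yes/no eCRF item, with no added patients or visits. The downside is that slightly more DLTs may be counted at 1.5 g, where two or more pause enrollment for DRT review.

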5.1.5 Recommended Dose of APR-246

The recommended dose of APR-246 in combination with venetoclax and rituximab represents the dose of APR-246 at or below the maximum intended dose, or the MTD, that results in the greatest apoptosis of circulating malignant cells in the monotherapy cycle.

The MTD of APR-246 will be defined as the dose at which <2 out of 6 patients experience DLT during the defined safety assessment period after administration of APR-246 in combination with venetoclax and rituximab. Up to 10 additional patients may be enrolled at the MTD, and at prior dose levels, to confirm the confidence at that dose level.

A DRT consisting of the Medical Monitor, Site Principal Investigators, and other clinical research personnel that the Sponsor may deem appropriate, will hold Data Review Meetings (DRMs) on an

interim basis at a frequency dependent on study accrual. At these meetings, the DRT will review any AEs, DLTs, and any available PK and PD data and make recommendations regarding the optimal dose of APR-246. All accumulated safety data will be discussed during DRMs. The optimal dose of APR-246 will be based upon the MTD and upon all accumulated safety data, PK/PD data, and preliminary efficacy data.

5.2 Dose Interruptions/Withholding

Study treatment, including APR-246, venetoclax, and/or rituximab, may be withheld from a patient based on the Investigator's decision in the event of intercurrent illness, AE, administrative reasons, or other reasons. If the patient's condition subsequently improves, or the situation that resulted in withholding study drug rectifies itself, the Investigator may resume dosing as soon as possible, unless the delay is more than 4 weeks. For study treatments held longer than 4 weeks, the Investigator should consult with the Medical Monitor before study treatments are resumed.

Dose management guidelines in [Table 5](#) should be followed for each occurrence of a grade ≥ 3 hematologic toxicity or those in [Table 6](#) for non-hematologic toxicity.

Table 5. Dose management guidelines for new onset hematologic toxicities

Toxicity	Occurrence	APR-246	Venetoclax	Rituximab
Grade 3 hematologic toxicity with fever and/or infection; or grade 4 hematologic toxicity	1 st occurrence • Hold all study treatments until blood count(s) return to baseline or grade ≤1 and fever and/or infection resolve if present. Treat promptly.	
 Consider reducing APR-246 by one dose level from starting dose for all future cycles of treatment if toxicity does not resolve to grade ≤1 within 7 days from onset date despite maximal medical intervention(s). If unable to reduce APR-246 dose, discuss with study Medical Monitor before resuming or discontinuing treatment. Initiate or reassess prophylaxis measures. Refer to Section 5.3.2.2 for supportive management guidelines specific to infection prophylaxis and neutropenia. 	
 Refer to Section 5.3.3.1 for venetoclax dose modification guidelines. 	
 Resume rituximab at same dose level once event resolves to baseline or grade ≤1, except in case of serious infection. For patients diagnosed with a serious grade ≥3 infection, rituximab should be permanently discontinued.
	2 nd occurrence • Hold all study treatments until blood count(s) return to baseline or Grade ≤1 and fever and/or infection resolve if present. Treat promptly.	
 Consider reducing APR-246 by one dose level from current dose for all future cycles of treatment if the toxicity does not resolve to grade ≤1 within 7 days from onset despite maximal medical intervention(s). If unable to reduce APR-246 dose, discuss with study Medical Monitor before resuming or discontinuing treatment. Initiate or reassess prophylaxis measures. Refer to Section 5.3.2.2 for supportive management guidelines specific to infection prophylaxis and neutropenia. 	
 Refer to Section 5.3.3.1 for venetoclax dose modification guidelines. 	
 Reduce rituximab dose from 500 mg/m² to 375 mg/m². If unable to reduce dose of rituximab, discuss with study Medical Monitor before resuming treatment. For patients diagnosed with a serious grade ≥3 infection, rituximab should be permanently discontinued.
	3 rd occurrence • Hold all study treatments until blood	
 Consult with study medical monitor to determine if further dose modifications of study treatment(s) are medically necessary or if study treatment(s) should be discontinued. 		

	
count(s) return to baseline or grade ≤1 and fever and/or infection resolve if present. Treat promptly.
	
Assess current prophylaxis measures being administered and adjust treatment plan as clinically indicated. Refer to Section 5.3.2.2 for supportive management guidelines specific to infection prophylaxis and neutropenia.
--	---	--

Administration of supportive measures such as G-CSF, platelet or blood transfusions, and/or antimicrobial therapy should be considered as clinically indicated.

Actions noted in table above for rituximab are specific to toxicities occurring during Cycles 2 through 7. Rituximab may be reduced by one dose level, from 500 mg/m² to 375 mg/m², when clinically indicated. Please consult with study Medical Monitor to discuss dose modification(s) for rituximab.

Patients experiencing 3 occurrences of the same toxicity should be discussed with the study Medical Monitor before study treatments are resumed.

Dose management guidelines for non-hematologic toxicities are provided below in [Table 6](#).

Table 6. Dose management guidelines for Grade 3 or 4 non-hematologic toxicities

Occurrence	APR-246	Venetoclax	Rituximab
1 st occurrence • Hold all study treatments until toxicity returns to baseline or grade ≤1. Treat promptly.	
Consider reducing APR-246 by one dose level from current dose for all future cycles of treatment if toxicity does not resolve to grade ≤1 within 7 days from onset date despite maximal medical intervention(s).If unable to reduce APR-246 dose, discuss with study Medical Monitor before resuming or discontinuing treatment.	Refer to Section 5.3.3.1 for venetoclax dose modification guidelines.	Resume rituximab at same dose level once event resolves to baseline or grade ≤1, except in case of serious infection. For patients diagnosed with a serious grade ≥3 infection, rituximab should be permanently discontinued.
2 nd occurrence • Hold all study treatments until toxicity returns to baseline or grade ≤1	
Consider reducing APR-246 by one dose level from starting dose for all future cycles of treatment.	Refer to Section 5.3.3.1 for venetoclax dose modification guidelines.	Reduce rituximab dose from 500 mg/m ² to 375 mg/m ² . If unable to reduce rituximab, discuss with study Medical Monitor before resuming or discontinuing rituximab. For patients diagnosed with serious grade ≥3 infection, rituximab should be permanently discontinued.
3 rd occurrence • Hold all study treatments until toxicity returns to baseline or grade ≤1. Treat promptly.	
Consult with study medical monitor to determine if further dose modifications of study treatment(s) are medically necessary or if study treatment(s) should be discontinued.		

Actions noted in table above for rituximab are specific to toxicities occurring during Cycles 2 through 7. Rituximab may be reduced by one dose level, from 500 mg/m² to 375 mg/m², when clinically indicated. Please consult with study Medical Monitor to discuss dose modification(s) for rituximab.

Treatment may be discontinued if a TEAE has not improved (to an acceptable grade) or resolved after ≥ 4 weeks, at the discretion of the Investigator. Please consult study Medical Monitor if this situation occurs.

Patients experiencing 3 occurrences of the same toxicity should be discussed with the study Medical Monitor before study treatments are resumed.

